11.2 DISPOSITION OF PATIENTS

Screened patients are defined as any patient who signed the informed consent.

Randomized patients consist of all screened patients, with a double-blind treatment kit number allocated and recorded in the IVRS/IWRS database, regardless of whether the treatment kit was used or not. Patients treated without being randomized or treated with a double-blind treatment kit before the randomization will not be considered as randomized and will not be included in any analysis population. The safety experience of patients treated and not randomized will be reported separately, and these patients will not be included in the safety population.

For any patient randomized more than once in Part 2 of the study, only the data associated with the first randomization will be used in any analysis population. The safety experience associated with any later randomization will be assessed separately.

11.3 ANALYSIS POPULATIONS

11.3.1 Efficacy populations

11.3.1.1 Intent-to-treat population

The Part 2 intent-to-treat (ITT) population will be defined as all randomized patients in Part 2. Patients from Part 1 who are rerandomized in Part 2 will not be included in Part 2 ITT population. The Part 2 ITT population is the primary analysis population for all efficacy endpoints. Patients will be analyzed in the treatment group to which they were randomized.

In addition, exploratory efficacy endpoints in Part 1 of the study will be described separately for non-Japanese and Japanese patients:

- The Part 1 non-Japanese ITT population will be defined as all non-Japanese randomized patients in Part 1. Patients will be analyzed in the treatment group to which they were randomized.
- The Part 1 Japanese ITT population will be defined as all Japanese randomized patients in Part 1. Patients will be analyzed in the treatment group to which they were randomized.

11.3.1.2 Per-protocol population

The Part 2 PP population will be defined as a subset of the Part 2 ITT population that excludes patients with major protocol deviations that potentially impact the primary efficacy endpoint. The criteria for exclusion of patients from the Part 2 PP population will be determined and documented prior to database lock. The Part 2 PP population will be used for sensitivity analysis purposes.

11.3.2 Safety population

The safety populations considered for safety analyses will be the randomized population who did actually receive at least one dose or part of a dose of the double-blind IMP. Patients will be analyzed according to the treatment actually received (GZ/SAR402671 or placebo).

Safety populations will be defined separately for Part 1 and Part 2 of the study:

- The Part 1 non-Japanese safety population will be defined as all non-Japanese randomized patients in non-Japanese Part 1 who received at least 1 dose of study medication in Part 1 of the study. All safety analyses in Part 1 of the study will be performed on the Part 1 non-Japanese safety population.
- The Part 1 Japanese safety population will be defined as all Japanese randomized patients in Part 1 who received at least 1 dose of study medication in Part 1 of the study. All safety analyses in Japanese Part 1 of the study will be performed on the Part 1 Japanese safety population.
- The Part 2 safety population will be defined as all randomized patients in Part 2 who received at least 1 dose of study medication in Part 2 of the study. Patients from Part 1 who are re-randomized in Part 2 will not be included in Part 2 safety population, and will be described separately. All safety analyses in Part 2 of the study will be performed on the Part 2 safety population.

In addition:

- Nonrandomized but treated patients will not be part of the safety populations, but their safety data will be presented separately.
- Randomized patients for whom it is unclear whether they took the study medication will be included in the safety population as randomized.
- For patients receiving more than one study treatment within the same part of the study, the treatment group allocation for as-treated analysis will be the one to which the patient was treated with the longest duration.

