5.2.2 Secondary objectives

To demonstrate the overall safety and tolerability of GZ/SAR402671 administered orally daily for 52 weeks in early-stage PD patients carrying a GBA mutation as compared to placebo.

To assess the pharmacodynamic response to daily oral dosing of GZ/SAR402671 in plasma and CSF as measured by GL-1 in early-stage PD patients carrying a GBA mutation over a 52-week period.

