If patients from Part 1 continue to meet eligibility requirements, and are willing to continue in the study, they may enroll in Part 2, but re-randomization will be required; furthermore, they will have to sign another informed consent form. All screening assessments will need to be repeated, except for the genetic screening, magnetic resonance imaging (MRI), LP, and ioflupane I-123 injection DaTSCAN (DAT scan), to confirm eligibility of patients from Part 1 to enroll in Part 2.

In Part 2, eligible patients will be stratified based on use of levodopa/PD medication (yes/no), cognitive function (Montreal Cognitive Assessment [MoCA] score <26 [yes/no]) and severe GBA mutation (yes/no). Patients will be randomized in a 1:1 ratio to receive GZ/SAR402671 or placebo for 52 weeks.

Part 2 will include 4 main periods: the up to 60-day screening period (Period 1), the 52-week blinded treatment period (Period 2), the 156-week duration long-term follow-up (LTFU) period (Period 3), and the 8-week post-treatment observation period (Period 4).

All patients who continue to meet inclusion criteria [I 06](#), [I 07](#), [I 08](#), and [I 09](#) and none of the exclusion criteria (exclusion criteria [E 02](#), [E 03](#), [E 05](#), and [E 06](#) will not need to be rechecked) at Week 52 will be eligible to receive GZ/SAR402671 treatment during the LTFU period (Period 3).

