6.2 DURATION OF STUDY PARTICIPATION

6.2.1 Duration of study participation for each patient

The maximum study duration per patient will be approximately 224 weeks (4.3 years, patients from Part 2 only) to 272 weeks (5.5 years, patients from Part 1 enrolling in Part 2), or to 288 weeks for Japanese patients (5.9 years, Japanese patients from Part 1 enrolling in Part 2).

Part 1: Dose escalation phase

The maximum study duration per patient will be approximately 50 weeks (or 66 weeks for Japanese patients), inclusive of the screening period. Three sequential cohorts are planned. Patients will receive either placebo or GZ/SAR402671 (4 mg, 8 mg, or 15 mg) for a minimum 8 weeks per cohort (and maximum of 36 weeks [or 52 weeks for Japanese patients], for Cohort 1).

Safety/tolerability data will be analyzed at the end of 4 weeks of treatment at each cohort before proceeding to the next cohort.

Part 2: Treatment phase

The total study treatment duration (Periods 2 and 3) is approximately 208 weeks (4 years).

The study comprises 4 main periods:

- Period 1: the up to 60-day screening period.
- Period 2: the 52-week double-blinded, randomized treatment period.
- Period 3: the 156-week LTFU period during which eligible patients will all receive GZ/SAR402671.
- Period 4: the 8-week post-treatment observation period with end of study visit.

Therefore, maximum duration for a patient will be approximately 224 weeks.

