6.5 DISCUSSION OF STUDY DESIGN

Current treatment options for PD patients, with or without GBA mutations, are limited due to side effects. Despite the many therapeutic agents available for the treatment of PD, patients can still experience intolerable disability due to disease progression. Thus, there is a high unmet medical need for better treatment alternatives in PD. Participation in this placebo-controlled study, with a novel mechanism of action, would present a unique opportunity for the patients. Patients will be allowed to start on PD therapy (only an immediate release levodopa formulation is allowed) or to continue to take their medication as usual (if already taking PD medication at study start).

Of note, PD prescription medications permitted (see [Section 8.8](#)) in this trial include:

- Dopamine replacement therapies (eg; levodopa/carbidopa).
- Dopamine agonists (eg; pramipexole, ropinirole, bromocriptine).
- Monoamine oxidase B inhibitors (eg; rasagiline).
- Catechol-O-methyltransferase inhibitors (eg; entacapone, tolcapone).
- Anticholinergics (eg; artane, cogentin).

The following points were taken into consideration in the design of the study:

- **Screening:** Sequencing of the GBA gene and genotyping for a LRRK2 (G2019S) mutation to ensure patient eligibility will be conducted from a collected whole blood sample even if historical results are available.
- **Randomization (Day 1, pre-dose):** To reduce the risk of imbalance between treatment groups with respect to cognitive function and PD medication. In Part 2, randomization will be stratified based on use of levodopa/PD medication (yes/no), cognitive function (MoCA score <26 [yes/no]) and severe GBA mutation (yes/no).
- **Long-term follow-up (Part 2):** Upon completion of the 52-week treatment period, eligible patients will be followed in an LTFU period for 36 months. Patients in the placebo arm will be switched to GZ/SAR402671 treatment after completing the Week 52 study visit. During the LTFU period, study drug assignment will remain blinded and patients will continue to be assessed by a blinded rater, thus collecting important information and

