11.4.3 Analyses of safety data

Safety data will be described separately for Part 1 and Part 2 of the study, and separately for Japanese and non-Japanese patients.

Safety and tolerability in the Japanese patients from Part 1 will be compared to the non-Japanese patients.

All safety analyses will be performed on the Part 1 safety population and Part 2 safety population respectively. The summary of safety results will be presented by treatment group actually received.

The baseline value is defined generally as the last available value before randomization, within each part of the study.

For all safety data, the observation period will be divided into 3 segments within each part of the study:

- The **pretreatment period** is defined as the time between the date of the informed consent and the first administration of double-blind IMP.
- The **on-treatment period** is defined as the period from the time of first IMP administration up to 6 weeks after the last administration of the IMP.
- The **post-treatment period** starts on the day after the end of the on-treatment period.

The following definitions will be applied to laboratory parameters, vital signs, and ECGs.

- The potentially clinically significant abnormality (PCSA) values are defined as abnormal values considered medically important by the Sponsor according to predefined criteria/thresholds based on literature review and defined by the Sponsor for clinical laboratory tests, vital signs, and ECGs.
- The PCSA criteria will determine which patients had at least 1 PCSA during the on-treatment period, taking into account all evaluations performed during the on-treatment period, including unscheduled or repeated evaluations. The number of all such patients will be the numerator for the on-treatment PCSA percentage.

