11.5.2 Two-step final analysis

The final analysis will be conducted in two steps:

- First step: analysis of the 52-week treatment period of Part 2 of the study:
 - The analysis of the 52-week treatment period of Part 2 of the study will be conducted when all patients from Part 2 have been randomized and have all their data up to Week 52 collected and validated, and will consist in the final analysis of the primary, secondary, and exploratory endpoints up to Week 52. The safety analysis will be performed on all safety data collected and validated at the time of the first analysis. This analysis will be conducted after a partial database lock and treatment unblinding.
- Second step: analysis up to Week 208 of Part 2 of the study:

The second analysis will be conducted at the end of the study and will consist of the final analysis up to Week 208. Specific analyses of efficacy and safety data up to Week 208 will be described in the SAP. This analysis will be conducted after the final database lock.

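### The longest-duration rule in section 11.3.2 spans all of Part 2, so the planned Week 52 switch mixes placebo and GZ/SAR402671 safety data at the step 1 analysis

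*Protocol*

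**What the plan says.** Protocol section 11.3.2 defines one Part 2 safety population, uses it for all Part 2 safety analyses, and groups patients by treatment actually received. Its last bullet covers anyone given two or more treatments in a single part, and fixes that "the treatment group allocation for as-treated analysis will be the one to which the patient was treated with the longest duration". The unit is the part, not the period.

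Section 6.1 places the 52-week blinded period and the 156-week long-term follow-up inside Part 2. Section 6.2.1 describes the latter as "the 156-week LTFU period during which eligible patients will all receive GZ/SAR402671", and section 6.5 says: "Patients in the placebo arm will be switched to GZ/SAR402671 treatment after completing the Week 52 study visit".

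Three further definitions decide which data enter the tables:

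- Section 11.4.3: the window for on-treatment data "is defined as the period from the time of first IMP administration up to 6 weeks after the last administration of the IMP".
- Section 11.4.1: exposure within a part runs from first to last dose, with no split by treatment.
- Section 11.5.2, first step: "The safety analysis will be performed on all safety data collected and validated at the time of the first analysis".

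Section 11.4.3.1 reports adverse events as patient counts and percentages, with the safety population of each treatment group as denominator. The objective to be served, in section 5.2.2, is "To demonstrate the overall safety and tolerability of GZ/SAR402671 administered orally daily for 52 weeks", compared with placebo.

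**The concern.** A placebo patient who enters Period 3 has received two study treatments in the same part, so the rule applies as a consequence of the design and not only after an error. Two kinds of misclassification follow at step 1.

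- A switcher whose time on GZ/SAR402671 exceeds the time on placebo moves to the GZ/SAR402671 column, taking along the placebo year and any events in it.
- A switcher with less Period 3 than Period 2 exposure stays in the placebo column, and events on active drug are counted as placebo events.

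The table meant to answer the 52-week safety objective would then compare neither the randomized groups nor the two treatments. The rule also blurs the comparison of safety between early and delayed starters announced in section 6.5, which needs the two original arms kept apart.

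**Working it through.** **Arm size.** Section 11.1 gives a difference of 4.06, SD 10.01, two-sided alpha 0.05, 80% power and 10% loss. Then 2 × (1.960 + 0.842)² × 10.01² / 4.06² = 95.4, so 96 evaluable per arm, and 96 / 0.9 = 106.7, so 107. A t-test needs one more: 97 / 0.9 = 107.8, so 108. The plan's 108 per arm is reproduced and not in dispute.

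**When a patient is relabelled.** Planned placebo time is 52 weeks and planned Period 3 time is 156 weeks. A switcher therefore changes column once total time from first dose passes about 104 weeks (2 years). The dose-regimen row of the synopsis gives 104 weeks for Period 3. That must be reconciled with the 156 weeks elsewhere, but both exceed 52, so the result here is the same.

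**Assumptions, because the protocol gives no figures.** Accrual is uniform over A years. Step 1 is cut when the last patient reaches Week 52, so follow-up ranges from 1 to A + 1 years. Dropout is 10% per year, so 0.9^t remain at t years. All who remain at Week 52 switch. The event rate is 5% per year in both arms (no drug effect).

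**Relabelled share.** A share (A − 1)/A of patients can have more than 2 years of follow-up, and 0.9² = 0.81 of them are still on treatment at 2 years. The relabelled share is (A − 1)/A × 0.81.

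**Active drug within the remaining placebo column.** For 12-month accrual, mean placebo time is ∫₀¹ 0.9^t dt = 0.949 years. Mean active time is ∫₁² 0.9^t (2 − t) dt = 0.434 years. The active share is 0.434 / 1.383 = 31%.

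**Crude risk ratio, 24-month accrual.** Mean time in an original arm is 0.949 + ∫₁³ 0.9^t (3 − t)/2 dt = 0.949 + 0.840 = 1.79 years. Relabelled patients average 2.48 years and the remaining placebo patients 1.32 (check: 0.405 × 2.48 + 0.595 × 1.32 = 1.79). The GZ/SAR402671 column averages (1.79 + 0.405 × 2.48) / 1.405 = 1.99 years. Averaging 1 − exp(−0.05 × time) within each column gives 9.4% against 6.3%, a ratio of about 1.5 with no drug effect.

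| Accrual (months) | Relabelled share | About, of 108 | Active share of remaining placebo person-time | Crude risk ratio, no true effect |
|---|---|---|---|---|
| 12 | 0% | 0 | 31% | 1.0 |
| 18 | 0.333 × 0.81 = 27% | 29 | 31% | 1.3 |
| 24 | 0.500 × 0.81 = 40% | 44 | 31% | 1.5 |
| 30 | 0.600 × 0.81 = 49% | 52 | 30% | 1.7 |

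Restricted to Period 2, the ratio is about 1.0 in every row.

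**The case against.** The strongest reply is that the bullet was meant for irregular cases. It closes a list whose other entries are patients treated without randomization and patients whose intake is unclear, and the section opens with double-blind IMP. Mis-dispensing is a plausible intent. Section 6.5 also plans to compare early with delayed starters on safety, which suggests that the arms were meant to stay apart. This stands as an account of intent. However, no sentence exempts the planned switch or limits the rule to Period 2, and section 6.5 keeps assignment blinded in Period 3, so the opening phrase does not exclude it. The plan in section 6.5 makes the conflict with the rule sharper.

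A second reply is that some wording points to a cut at Week 52. Step 1 is headed as the analysis of the 52-week period, and section 11.4.3.1 counts repeat events once per treatment period. But the safety sentence of step 1 is wider than its heading, and section 8.8.1 uses treatment period for Periods 2 and 3 together. This does not settle the matter.

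A reader might infer that the placebo group all but disappears: under the same assumptions 81% would be relabelled at full follow-up, leaving about 20 of 108, with a crude ratio near 3.4. Section 11.5.2 leaves the specific Week 208 analyses to the SAP, so those figures cannot be charged to this protocol.

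A reader might also infer that the bias could run in either direction. That is not shown: every ratio computed here is 1.0 or higher. The excess comes from crude percentages over unequal follow-up; in the same no-effect simulation the exposure-adjusted rate ratio stays at 0.99 to 1.01. Crude percentages are, however, what section 11.4.3.1 plans.

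**Conclusion.** The point holds for step 1. Followed literally, the protocol's grouping rule, on-treatment window and data scope mix placebo and active-drug safety data, and they conflict with the 52-week objective in section 5.2.2 and with the early- versus delayed-start comparison in section 6.5.

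The size depends on accrual, dropout, transition and event rates that the protocol does not give. Not every switcher is relabelled, only those with more Period 3 than Period 2 exposure. If accrual took 12 months no one would be relabelled at step 1 and the crude ratio would be 1.0. Even then, about 31% of the person-time labelled placebo would be on active drug, so the second misclassification does not depend on long accrual. Efficacy is unaffected, because the ITT population is analysed as randomized.

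**What to change.** - **Section 11.3.2:** limit the longest-duration rule to treatment received in Period 2, and state that the planned switch after Week 52 does not change a patient's group.
- **Sections 11.4.1, 11.4.3 and 11.5.2:** for the placebo-controlled comparison, end both exposure and the on-treatment window at the first Period 3 dose, or 6 weeks after the last dose for patients who do not enter Period 3.
- **Period 3 safety:** tabulate it separately by original arm (early start and delayed start).

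The planned comparison then stays at 108 against 108, and the rule acts only on genuine treatment errors. The cost is wording in four sections and one extra set of safety tables, with no new data. The wording should be settled before the step 1 unblinding. Baseline reset for switchers and exposure-adjusted rates can be left to the SAP.

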11.3.3 Pharmacokinetics/pharmacodynamics population

The PK and pharmacodynamics populations will be defined as all patients who received at least 1 dose of GZ/SAR402671 and who have at least one PK or pharmacodynamics assessment, respectively.

Pharmacokinetics and pharmacodynamics data will be described separately for Part 1 and Part 2 of the study, and separately for non-Japanese and Japanese patients:

- The Part 1 non-Japanese pharmacodynamics and PK populations will be defined as all non-Japanese patients in Part 1 who received at least 1 dose of GZ/SAR402671 and who have at least one pharmacodynamics or PK assessment, respectively.
- The Part 1 Japanese pharmacodynamics and PK populations will be defined as all Japanese patients in Part 1 who received at least 1 dose of GZ/SAR402671 and who have at least one pharmacodynamics or PK assessment, respectively.
- The Part 2 non-Japanese pharmacodynamics and PK populations will be defined as all patients in Part 2 who received at least 1 dose of GZ/SAR402671 and who have at least one pharmacodynamics or PK assessment, respectively. Patients from Part 1 who are rerandomized in Part 2 will not be included in Part 2 pharmacodynamics and PK populations, and will be described separately.
- The Part 2 Japanese pharmacodynamics and PK populations will be defined as all Japanese patients in Part 2 who received at least 1 dose of GZ/SAR402671 and who have at least one pharmacodynamics or PK assessment, respectively. Patients from Part 1 who are rerandomized in Part 2 will not be included in Part 2 Japanese pharmacodynamics and PK populations, and will be described separately.

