	
terminations/unevaluable patients.
 
Of note, the approximate 27 early-stage PD patients carrying a GBA mutation from Part 1 may be re-randomized and participate in all of the assessments in Part 2 of this study; however, they will not contribute to the primary efficacy, safety, PK and pharmacodynamics analyses, and will be described separately.
 
Analysis populations
 
Part 1: Dose escalation phase
 
The Part 1 safety population is defined as all randomized patients in Part 1 who received at least 1 dose of study medication. All safety analyses in Part 1 will be performed on the Part 1 safety population. Patients will be summarized based on the treatment they received.
 
The Part 1 Japanese safety population will be defined as all Japanese randomized patients in Part 1 who received at least 1 dose of study medication in Part 1 of the study. All safety analyses in Japanese Part 1 of the study will be performed on the Part 1 Japanese safety population.
 
The Part 1 pharmacodynamics and PK populations will be defined as all patients in Part 1 who received at least 1 dose of GZ/SAR402671 and who have at least one pharmacodynamics or PK assessment, respectively.
 
The Part 1 Japanese pharmacodynamics and PK populations will be defined as all Japanese patients in Part 1 who received at least 1 dose of GZ/SAR402671 and who have at least one pharmacodynamics or PK assessment, respectively.
 
Part 2: Treatment phase
 
The Part 2 intent-to-treat (ITT) population is defined as all randomized patients in Part 2. Patients from Part 1 who are re-randomized in Part 2 will not be included in Part 2 ITT population. The Part 2 ITT population is the primary analysis population for all efficacy endpoints. Patients will be analyzed in the treatment group to which they were randomized.
 
The Part 2 safety population is defined as all randomized patients in Part 2 who received at least 1 dose of study medication in Part 2 of the study. Patients from Part 1 who are re-randomized in Part 2 will not be included in Part 2 safety population, and will be described separately. All safety analyses in Part 2 will be performed on the Part 2 safety population. Patients will be summarized based on the treatment they received.
 
The Part 2 pharmacodynamics and PK populations will be defined as all patients in Part 2 who received at least 1 dose of GZ/SAR402671 and who have at least one pharmacodynamics or PK assessment, respectively. Patients from Part 1 who are re-randomized in Part 2 will not be included in Part 2 pharmacodynamics and PK populations, and will be described separately.
 
The Part 2 Japanese pharmacodynamics and PK populations will be defined as all Japanese patients in Part 2 who received at least 1 dose of GZ/SAR402671 and who have at least one pharmacodynamics or PK assessment, respectively. Patients from Part 1 who are rerandomized in Part 2 will not be included in Part 2 Japanese pharmacodynamics and PK populations, and will be described separately.

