10.1.2.10 Long term follow-up period (Period 3)

Patients who complete the 52 weeks of double-blinded treatment and who continue to meet inclusion criteria [I 06](#), [I 07](#), [I 08](#), and [I 09](#) and none of the exclusion criteria (exclusion criteria [E 02](#), [E 03](#), [E 05](#), and [E 06](#) will not need to be rechecked) will be eligible to enroll to the LTFU period (Period 3) where they will continue to receive appropriate monitoring and will receive GZ/SAR402671 treatment after Visit 9. It is important to note that patients will not be informed of when the switch will occur, nor will the person(s) performing any of the evaluations.

Throughout Period 3, a visit window of ± 7 days for all visits is acceptable using Day 1 as reference.

During this period, a clinic visit will be scheduled at 6-month intervals (Weeks 78, 104, 130, 156, 182, and 208) and patients will receive GZ/SAR402671, orally, at the clinic. For Japanese patients only, additional clinic visit will be scheduled at Weeks 65, 91, 117, 143, 169, and 195 (Visits 9.1, 10.1, 11.1, 12.1, 13.1, and 14.1) in addition to the above 6-month interval visits.

Before dosing, the following assessments will be performed at each study visit (every 6 months), as listed in the study flow chart, [Section 1.3.3](#), which should be done in the following order:

- Whenever possible, the following scales and questionnaires should be done prior to clinical interaction with the Investigator:
 - BDI-II ([Appendix L](#))
 - PDQ-39 ([Appendix O](#))
 - EQ-5D ([Appendix P](#))
 - HRPQ ([Appendix R](#))
 - FES ([Appendix Q](#))
- MDS-UPDRS, including H&Y ([Appendix F](#))
- PD-CRS ([Appendix G](#))
- Other questionnaires and scales
 - MoCA ([Appendix I](#))

- Oral SDMT ([Appendix J](#))
- TMT-A; TMT-B ([Appendix K](#))
- Review of concomitant medications (every 3 months [13 weeks] for Japanese patients only)
- General neurological examination
- Visual acuity check, slit lamp examination, and fundoscopy without pupil dilation at Visits 10, 12, and 14; at Visits 11, 13, and 15, patients will have a full ophthalmology examination and photography (must be performed after the neurological examination)
- Vital signs: systolic and diastolic blood pressure (mm Hg), heart rate (bpm), respiratory rate (breaths/minute), and temperature (°C) (every 3 months [13 weeks] for Japanese patients only)
- Urine pregnancy test (for WOCBP)

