11.4.4 Analyses of pharmacokinetic and pharmacodynamic variables

Pharmacokinetic and pharmacodynamic data will be described separately for Part 1 and Part 2 of the study, and separately for Japanese and non-Japanese patients.

Pharmacokinetics and pharmacodynamics in the Japanese patients from Part 1 will be compared to the non-Japanese patients.

Pharmacodynamic parameters will be summarized and compared between GZ/SAR402671 and placebo administration using descriptive statistics at each time point, including assessment of observed values, and percent change from baseline. p-Values for statistical comparisons will be provided for descriptive purpose. Plasma PK parameters will be summarized using descriptive

statistics and also analyzed using noncompartmental methods. CSF exposure of GZ/SAR402671 will be summarized using descriptive statistics at each time point.

Pharmacokinetic parameters may be estimated for metabolites using noncompartmental methods and reported for individual patients and summarized using descriptive statistics.

With respect to biomarkers, levels of plasma, serum or CSF biomarkers, as well as changes from baseline, will be summarized descriptively by time point.

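### The pharmacodynamic populations require a dose of GZ/SAR402671, which contradicts the planned comparison with placebo

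*Protocol*

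**What the plan says.** Section 11.3.3 gives a single rule for two populations: "The PK and pharmacodynamics populations will be defined as all patients who received at least 1 dose of GZ/SAR402671", each also needing at least one assessment of its own kind. The same dose condition appears in each Part 1 and Part 2, Japanese and non-Japanese version. The synopsis, under analysis populations, agrees: "The Part 2 pharmacodynamics and PK populations will be defined as all patients in Part 2 who received at least 1 dose of GZ/SAR402671".

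Section 11.4.4 then describes the analysis: "Pharmacodynamic parameters will be summarized and compared between GZ/SAR402671 and placebo administration using descriptive statistics at each time point". It adds: "p-Values for statistical comparisons will be provided for descriptive purpose". The synopsis states the same comparison for Part 1 and Part 2.

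For Part 2 the analysis serves the secondary objective in Section 5.2.2: "To assess the pharmacodynamic response to daily oral dosing of GZ/SAR402671 in plasma and CSF as measured by GL-1".

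Placebo patients can receive GZ/SAR402671 within Part 2 only in Period 3. Section 6.5 says: "Patients in the placebo arm will be switched to GZ/SAR402671 treatment after completing the Week 52 study visit". Section 10.1.2.10 limits who may enter: "Patients who complete the 52 weeks of double-blinded treatment and who continue to meet inclusion criteria", together with a re-check of most exclusion criteria.

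**The concern.** The population rule and the planned comparison cannot both be followed. During Part 1 and during Period 2 of Part 2, a placebo patient receives no GZ/SAR402671. A set built on receipt of that drug therefore leaves the comparison without a comparator.

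There is a way for some placebo patients to enter the Part 2 set. Section 6.1 makes Period 3 part of Part 2, so a placebo patient dosed with GZ/SAR402671 after Week 52 meets the literal wording. Inclusion in the Week 26 and Week 52 comparisons would then depend on events after those samples were due: completing 52 weeks and passing the re-check. Patients on active treatment face no such condition, since they qualify from their first dose once they have an assessment. The comparison would set all dosed and assessed active patients against a selected group of placebo completers, and the balance given by randomisation would be lost.

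At stake is the evidence that the drug lowers GL-1 in plasma and CSF relative to placebo, which supports interpretation of the clinical result.

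**Working it through.** **1. Does the plan intend pharmacodynamic data from both arms?** Table 1 (Section 9.4.1) gives patients and sampling time points. Multiplying them reproduces its totals exactly.
- Part 2 plasma/serum: 216 × 7 = 1512. Part 2 CSF: 216 × 2 = 432.
- Part 1 plasma/serum: 15 × 3 = 45 and 12 × 3 = 36. Part 1 CSF: 15 × 2 = 30 and 12 × 2 = 24.

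The 216 is 108 per arm (Section 11.1), and the 15 and 12 include 3 placebo patients each. Samples are planned from both arms.

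**2. Could the drug name mean either study treatment?** No. Section 8.1 distinguishes GZ/SAR402671 from matching placebo. Section 11.3.2 defines the safety populations by study medication or double-blind IMP, which keeps placebo patients. Section 11.3.3 uses neither term.

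**3. Where does an active-only rule fit?** Section 9.4.2.3 restricts the drug-concentration assay to patients on active treatment. That supports an active-only PK set. It gives no reason for an active-only pharmacodynamic set.

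**4. Who remains, counting only dosing in Part 1 or in Period 2?**
- Part 1: 12 + 9 = 21 of 27 patients. All 3 + 3 = 6 placebo patients are out.
- Part 2: 108 active and 0 of 108 placebo.
- Part 2 samples inside the population: at most 108 × 7 = 756 of 1512 plasma/serum and 108 × 2 = 216 of 432 CSF, half in each case.

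**5. Who remains in Part 2 if a Period 3 dose counts?** With r the proportion of placebo patients entering Period 3, the number dropped is 108 × (1 − r). The document does not give r, so these values are assumptions:

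| Assumed entry r | Placebo kept | Placebo dropped |
|---|---|---|
| 100% | 108 | 0 |
| 90% | 97 | 11 |
| 80% | 86 | 22 |
| 70% | 76 | 32 |
| 50% | 54 | 54 |

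**6. Can the 10% in Section 11.1 supply r?** That figure belongs to the sample size. With a difference of 4.06, SD 10.01, two-sided alpha 0.05 and 80% power, the t-test needs 97 per arm, and 97 / (1 − 0.10) = 107.8, which rounds up to the stated 108. The 10% is an allowance for early termination or unevaluable patients on the primary endpoint, so it does not estimate entry to Period 3.

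**The case against.** The strongest reply is that the intent is plain and little depends on it. The placebo comparison is stated twice and the samples are counted from both arms. Section 11.4.4 does not name the pharmacodynamic population as its analysis set, although Section 11.4.3 names the safety populations. An analyst facing an empty placebo column would notice at once. The text looks like a joint definition in which a PK condition spread to pharmacodynamics. This is a fair account of how the error arose, but no other section supplies a set that keeps placebo patients, so the contradiction stands.

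The reply is right about weight. A reader might infer that a secondary endpoint or a confirmatory test is lost. The documents do not support that. Section 9.2.2 lists only PD-CRS, MDS-UPDRS Parts I+II+III and Hoehn and Yahr as secondary endpoints. GL-1 is listed among the exploratory endpoints, lies outside the hierarchy in Section 11.4.2.3, and has descriptive p-values.

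Three further inferences should be resisted:
- That the protocol plans to admit placebo patients through Period 3. The wording permits it, but no section says so.
- That about 11 of 108 placebo patients would be lost at a rate the plan itself gives. That number corresponds to the assumed 90% row only.
- That no active patient with a sample is excluded. A patient randomised to active treatment with a pre-dose sample but no dose is excluded, as are Part 1 patients re-randomised to active treatment.

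**Conclusion.** The contradiction is real and is fixed in the protocol text; it is not a detail left for the SAP. On dosing within Part 1, 0 of 6 placebo patients qualify. On Period 2 dosing, 0 of 108 qualify in Part 2. If Period 3 dosing counts, the placebo side is limited to patients who completed Week 52 and were judged eligible. The number lost then depends on an entry rate that the document does not give: 0 to 54 over an assumed 100% to 50%.

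The consequence is limited to the GL-1 secondary objective and the exploratory biomarkers. The primary efficacy analysis uses the ITT population, the safety analysis has its own populations, and the sample size and type I error control do not involve these sets. It should be corrected, but it does not threaten the trial's main conclusion.

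**What to change.** Separate the two definitions in Section 11.3.3 and in the synopsis, in every Part 1 and Part 2, Japanese and non-Japanese version.

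- **Pharmacodynamic population:** all randomised patients with at least one dose of double-blind IMP (GZ/SAR402671 or placebo) in the relevant part and at least one pharmacodynamic assessment. Group them by the double-blind treatment received in that part: Part 1 treatment for Part 1, Period 2 treatment for Part 2. Keep the existing rule that Part 1 patients re-randomised in Part 2 are excluded from the Part 2 set and described separately.
- **PK population:** unchanged, requiring at least one dose of GZ/SAR402671 and at least one PK assessment.

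Name the pharmacodynamic population in Section 11.4.4 as the set for the placebo comparison. Settle this before the partial database lock and unblinding in Section 11.5.2. If the SAP already separates the sets, align the protocol with it.

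The cost is wording only. Table 1 already provides for samples from both arms, so no patient, visit or sample is added.
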